## 3. OVERALL DESIGN AND FLOW CHART

Overall Design

The investigation is designed as an open, randomized, non-inferiority, multi-centre investigation. A total of 212 subjects will be randomised. Subjects to be included will suffer from a moderately or strongly exuding venous or mixed ulcer of predominantly venous origin with at least 70% of the wound bed covered with slough at baseline. Both in and out-subjects will be eligible. Each subject will be treated according to the local clinical routine and evaluated during a total treatment period of maximum 6 weeks or until the wound is healed.

At least 50 subjects (from the wound care centers owned by GVW in Germany) out of the total 212 subjects will be followed for maximum 24 weeks to investigate wound closure. Subjects will either be randomized to Exufiber® or Aquacel Extra using a centralized randomization. The secondary dressing will be according to the normal praxis at each clinic and preferably one secondary dressing by treatment group should be chosen to be used for all subjects although no active dressings such as anti-microbial dressings are allowed. Simple gauzes or polyurethane (PU) films are recommended (see schedule of assessment for details). Patients should be treated with a recognized efficient compression system (e.g. multicomponents such as 2-, 3- or 4-LB (two-, three- or four-layer bandage) or SSB (short stretch bandage)). The nature of applied bandages will be captured in the electronic Case Report Form (eCRF).

Visits are planned for baseline followed by 1, 2, 3, 4 and 6 weeks post treatment. The subgroup of at least 50 subjects (from the wound care centers owned by GVW in Germany) will also be followed at week 8, 12, 16, 20, and 24 post treatment or until wound is healed if earlier. Dressing changes in-between visits are allowed and should be carried out according to normal praxis/intended use e.g. when the dressing is saturated. These can be performed at the subject's home according to normal routine. At each dressing change, the wound is to be inspected and cleaned exclusively with normal saline or warm water (or Actimaris Rinsing Solution). When the wound is dry, Exufiber® is no longer applicable. The treatment should then continue with the secondary dressing or other suitable dressing according to local guidelines and compression followed until end of investigation at 6 or 24 weeks or earlier if the wound heals. Aquacel Extra is also intended for dry wounds but should be used in the same way as Exufiber® for consistency.

A record (dressing log) for Exufiber® or Aquacel Extra will be filled in to capture all dressing changes at the scheduled visits including secondary dressing and compression applied. The number of dressing changes in-between scheduled visits will be asked for at each visit as well as number of dispensed and returned dressings. A nurse book can be used to collect the data related to the dressing change (number of dressings, reason for dressing change) between scheduled visits.

Subjects will be screened on a daily basis and if they seem evaluable they will be given a patient information.

### 3.1.1 Schedule of Assessment

Week number	Week 0 (Baseline)	Week 1,2,3,4 and 6	Unscheduled visits*	Week 8-24**
Visit window	NA	± 2 days	NA	± 3 days
Informed Consent	√			
Inclusion and Exclusion Criteria	√			
Subject Demographics including vital signs	√			
Relevant medical condition and surgical procedure	√			
Current treatment	√			
History of Leg ulcer	√			
Wound status (colorimetric scale)	√	√		√
Condition of peri-wound skin	√	√		√
Signs and symptoms of local infection	√	√		
Pain assessment (VAS) a	√	√		
Wound preparation (cleansing b /debridement)	√	√	√	√
Dressing application c	√	√ d	√	√ d
Dressing removal e		√	√	√
EQ-5D-3L	√	√ f		√ f
Photograph g	√	√		√
Clinician's evaluation	√	√		
Subject's evaluation		√		
Technical performance		√		

Week number	Week 0 (Baseline)	Week 1,2,3,4 and 6	Unscheduled visits*	Week 8-24**
Medicine log	↓	↓	↓	↓
Adverse Events	↓	↓	↓	↓

\*: Unscheduled visits can be performed at the clinic if/when deemed necessary for dressing changes. Cleansing should be performed according to intended use. Only saline and warm water or Actimaris Rinsing Solution are allowed on the wound. Debridement is not allowed at unscheduled visits. The dressing log should only be filled in at scheduled visits.

\*\*: At least 50 subjects from the wound care centers owned by GWV in Germany, out of the total 212 subjects, will be followed for 24 weeks or until wound is healed if earlier. Visits will be performed once a month e.g. at week 8, 12, 16, 20 and 24.

a: Document any analgesics used under Medicine Log.

b: Only saline and warm water or Actimaris Rinsing Solution allowed on the wound. Local applications such as pastes and corticosteroids are allowed outside the lesions. Debridement is not allowed at unscheduled visits.

c: Exufiber® or Aquacel Extra should be applied after cleaning/debridement and according to the randomisation schedule. Secondary dressing should be applied according to hospital praxis, simple gauzes or PU films are preferred and active dressings such as anti-microbial dressings are not allowed. Details to be recorded in the eCRF. The ulcer should be treated with a recognized efficient compression system (e.g. multicomponents such as 2-,3- or 4-LB or SSB). Record the nature of applied bandages in the eCRF.

d: Not at week 6/24 (i.e. final visit).

e: The number of dressing changes in-between visits should be captured at each scheduled visit, only changes in the dressing routine will be captured at each scheduled visit.

f: Only at week 4, 6 and 24.

g: Please see Appendix C for a detailed instruction of when photos should be taken.

Please include measuring scale (ruler) with date, subject number and visit number and please respect the confidentiality of the subject by not including any personal numbers or identifying characteristics. A digital camera will be distributed by Mölnlycke Health Care at or before the initiation. The ruler is used for calibration of the photograph for objective measurements in the PictZar program. The PictZar analysis including wound size measurement will be performed on the photos taken after debridement at week 0, 4 and 6 or the final visit if sooner. For subjects that are followed up to 24 weeks, an additional PictZar analysis including wound size measurement will be performed on photos taken at week 24 (or last visit).

Please refer to Appendix D for a complete digital photography guideline.

## 4. POPULATIONS OF ANALYSIS SETS

### 4.1 Intention to treat Population

The Intention to Treat (ITT) population will include all randomised subjects with at least one follow-up measurement. The ITT population will be defined at the clean file meeting.

### 4.2 Per Protocol Population

The Per Protocol (PP) population will include all subjects in the ITT population with a wound area measurement at baseline and at week 6, or earlier if wound is healed prior to week 6, and without significant protocol violations. Subjects identified as protocol violators will be documented and agreed between Mölnlycke Health Care and statistician at the clean-file meeting.

### **4.3 Safety population**

The population for the assessment of safety will include all randomised subjects with application of the dressing

## **5. VARIABLES OF ANALYSIS**

### **5.1 Subjects Characteristics**

- Age
- Gender
- Race (where applicable)
- Mobility
- Height, weight and BMI (calculated)
- Duration of leg ulcer and wound location
- Latest ABPI value
- Recurrent ulcer
- Current dressing and current compression

### **5.2 Medical condition and Surgical history**

- Ongoing relevant medical conditions
- Relevant surgical history

### **5.3 Efficacy variables**

#### **5.3.1 Primary Efficacy Endpoint**

Primary efficacy variable is relative reduction of wound area (%) from baseline to end of investigation (up to 6 weeks) measured by the validated system PictZar on the photos taken after debridement at week 0, week 4 and week 6 (or final visit).

A supportive primary efficacy variable will be the relative reduction of wound area (%) from baseline to end of investigation (up to 6 weeks) with measurements from the supportive blind review done by an independent French expert.

#### **5.3.2 Secondary Efficacy Endpoints**

- Wound area reduction (absolute change in cm^2) from baseline to end of investigation (up to 6 weeks). Also measured by PictZar.
- Linear advance of the wound margin according to Gilman's formula (Cardinal et al, 2008) based on the digital photos and calculated by PictZar
- Relative reduction of sloughy tissue after the 6-week treatment period or when the wound is dry/healed. (Measured with PictZar and according to the judgment of the clinician)
- Debrided wound at end of investigation

- ✓ at least 70% of the wound surface area covered with granulation tissue confirmed using PictZar
- Changes from baseline in the condition of the peri-wound skin measured by the following variables; maceration, redness/irritation, blistering, skin stripping, trauma to wound edges
- The level of pain in connection to dressing changes and during debridement (measured by VAS 0-100mm)
  - ✓ Any intake/application of analgesics within 3 hours?
  - ✓ Pain before dressing assessment
  - ✓ Pain DURING dressing removal
  - ✓ Pain during debridement
- Wound status
  - Exudate amount and nature
  - Wound bed aspect after debridement/cleansing
    - ✓ % of fibrin tissue
    - ✓ % of granulation tissue
    - ✓ % of epithelialization
    - ✓ % other
- Clinician's opinion in relation to the dressing
  - ✓ Ease of application of the dressing
  - ✓ Ease of removal of the dressing
  - ✓ Non-adherence to wound bed at removal of primary dressing
  - ✓ Non-adherence to peri-wound skin at removal of primary dressing
  - ✓ Flexibility of dressing
  - ✓ Overall experience of the dressing
  - ✓ Conformability to the wound
- Subject's opinion in relation to the dressing
  - ✓ Experience anxiety during study product change
  - ✓ Ease of movement while wearing study product
  - ✓ Study product remained in place while wearing it
  - ✓ Sting or burning while wearing study product

- ✓ Comfortable to wear
  - ✓ Would you use this product again (only at last visit)
- Technical performance in relation to the dressing
  - ✓ Presence of residual in the wound after dressing removal
  - ✓ Ability to absorb exudate
  - ✓ Ability to retain exudate within the study product
  - ✓ Ability to absorb blood
  - ✓ Ability to keep slough and blood within study product
- Health related quality of life using EQ-5D-3L at baseline, 4 and 6 weeks
  - ✓ Mobility
  - ✓ Self-care
  - ✓ Usual activities
  - ✓ Pain discomfort
  - ✓ Anxiety/depression
  - ✓ Single Index from the five questions
  - ✓ VAS 0-100 of health status
- Cost effectiveness and health economics will be measured using EQ-5D-3L and dressing material used
- No of dressing changes per week and during the total treatment period

Ancillary endpoint to evaluate (extended substudy 24 weeks);

- ✓ Wound area reduction (compared to baseline) of 80% or more
- ✓ Wound closure (100% epithelialization confirmed by photo) rate
- ✓ Health related quality of life using EQ-5D-3L

### 5.3.3 Safety Measurements and Variables

The safety variables are Adverse Event (AE) / Adverse Device Effect (ADE), Serious Adverse Event (SAE)/Serious / Adverse Device Effect (SADE), and Device Deficiencies (DD). The definitions and procedures for reporting are presented in section 8 of the CIP.

## 6. STATISTICAL METHODOLOGY AND SAMPLE SIZE DETERMINATION

### 6.1 General Methodology

In this non-inferiority study the primary efficacy analysis will be constructing a two sided 95% confidence interval, using Fisher's non-parametric permutation test, for between-treatment differences (Exufiber® - Aquacel® Extra) in the mean percentage wound area reduction from

baseline to 6 weeks follow-up. This means that if the lower limit of this confidence interval is greater than 12% non-inferiority will be established.

All the main efficacy analyses will be performed on the PP population. Complementary efficacy analyses will be performed on the ITT population for further confirmation. The ITT and PP analyses will have to provide the same results to establish the non-inferiority. All safety analysis will be performed on the safety population.

Superiority can be concluded if the lower bound of a two sided 95% confidence interval for between-treatment differences (Exufiber® - Aquacel® Extra) in the mean percentage wound area reduction from baseline to 6 weeks follow-up does not overpass zero.

There will also be a second blinded assessment carried out by an independent French expert (not using the PictZar system) that will support the primary efficacy analysis done by PictZar.

For comparison between the two randomized groups regarding baseline variables and secondary efficacy variables Fisher's non-parametric permutation will be used for continuous variables, Mantel-Haenszel chi-square test for ordered categorical variables, Pearson Chi-square test for non-ordered categorical variables and Fishers exact test will be used for dichotomous variables.

For continuous variables 95% confidence intervals based on Fisher's non-parametric permutation tests will be calculated for the mean differences between the two groups. For dichotomous variables 95% confidence intervals for difference in proportion will be calculated.

If significant differences are found in baseline variables between the two treatments, complementary analyses of treatment adjusted for these baseline variables will be performed. These adjustments for baseline variables will be done with multiple logistic regression analyses for dichotomous variables and with covariance analysis for continuous variables.

For the primary efficacy endpoint, and for applicable secondary efficacy endpoints, last observation carried forward will be applied for the last follow-up measurement before 6 weeks and forward to the final 6 week measurement. No other imputation methods will be used.

For the primary efficacy endpoint a sensitivity analysis will be performed using complete case.

Frequency tables (including n, mean, median, standard deviation, minimum and maximum for continuous variables and n, frequency and percentage for categorical values) will be provided for all variables by treatment, as well as for the changes from baseline within each treatment by treatment.

Sub-group analyses by country will be performed.

Exploratory interaction analyses will be performed for primary efficacy variable and selected secondary variables between study groups and selected baseline variables in order to find subgroups where the effect of Exufiber in relation to Aquacel Extra is significantly improved. All statistical tests will be two-sided and conducted at the 5% significance level. All analysis will be performed with SAS software version 9.4 or later.

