## **4.8 Statistical Methods and Determination of Sample Size**

### **4.8.1 Statistical Evaluation**

The intent-to-treat (ITT) population is defined as all randomised patients with at least one follow up planimetry value (from the validated tool PictZar) and the per-protocol (PP) population as all patients with a wound area measurement till the fourth week of follow-up, at least. Subjects with significant protocol deviations will be excluded from the PP population.

PictZar has received 510k notification and is compliant with CFR Part 11.

In this non-inferiority study the primary efficacy analysis will be constructing a two sided 95% confidence interval, using Fisher's non-parametric permutation test, for between-treatment differences (Exufiber® - Aquacel® Extra) in the mean percentage area change from baseline to 6 weeks. This means that if the lower limit of this confidence interval is greater than 12% non-inferiority will be established.

All the main efficacy analyses will be performed on the PP population. Complementary efficacy analyses will be performed on the ITT-population for further confirmation. The ITT and PP analyses will have to provide the same results to establish the non-inferiority. All safety analysis will be performed on the safety population.

Superiority can be concluded if the lower bound of a two sided 95% confidence interval for between-treatment differences (Exufiber® - Aquacel® Extra) in the mean percentage area change from baseline to 6 weeks does not overpass zero.

There will also be a second blinded assessment carried out (not using the PictZar system) that will support the main analysis done by PictZar.

For secondary variables Fishers exact test for dichotomous variables, Mantel-Haenszel chi-square test for ordered categorical variables and Pearson Chi-square test for non-ordered categorical variables and Fisher's non-parametric permutation will be used for continuous variables.

If necessary adjustment for baseline variables will be done with multiple logistic regression for dichotomous variables and with covariance analysis for continuous variables.

All statistical tests will be two-sided and conducted at the 5% significance level.

A sub-group analysis by country will be performed.

For the primary endpoint last observation carried forward will be applied for the final measurement. No other imputation methods will be used.

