## **6.3 Efficacy Analyses**

### **6.3.1 Primary efficacy analysis**

In this non-inferiority study the primary efficacy analysis will be constructing a two sided 95% confidence interval, using Fisher's non-parametric permutation test, for between-treatment differences (Exufiber® - Aquacel® Extra) in the mean percentage wound area reduction from baseline to 6 weeks follow-up using PictZar on the PP population. A corresponding complementary two sided 95% confidence interval on the ITT population will also be constructed. If the lower limits of both these confidence intervals are greater than 12% non-inferiority will be established.

For the primary efficacy endpoint last observation carried forward will be applied for the last follow-up measurement before 6 weeks and forward to the final 6 week measurement. Supporting identical analyses will be performed on the primary efficacy variable using the values from a second supportive blind review of the independent French expert.

Also a sensitive analysis using PictZar will be performed using complete cases.

Tables will be given for wound area by visit and analysed between treatments and for wound area reduction (%) from baseline to each visit and analysed between treatments.

Superiority can be concluded if the lower bound of a two sided 95% confidence interval for between-treatment differences (Exufiber® - Aquacel® Extra) in the mean percentage wound area reduction from baseline to 6 weeks follow-up using PictZar on the ITT population does not overpass zero.

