### **6.3.2 Secondary efficacy analyses**

All secondary efficacy variables given in section 5.3.2 above will be analysed between Exufiber® and Aquacel® Extra on both the PP population and the ITT population according to the statistical methods given in section 6.1. The main analyses will be performed at the 6 weeks follow-up and /or change from baseline to 6 weeks follow-up. For applicable secondary efficacy endpoints last observation carried forward will be applied for the last follow-up measurement before 6 weeks and forward to the final 6 weeks measurement.

Where appropriate, the statistical analyses will also be performed at the 4 week follow-up and /or change from baseline to 4 week follow-up.

For continuous variables and dichotomous variables 95% confidence intervals will be calculated for the mean difference between the two study groups.

Tables with descriptive statistics will be given for all secondary efficacy variables by visit, by treatment group and change from baseline to each visit

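### The secondary difference tests default to a per-protocol lead set that drops subjects who leave unhealed, and only one of three relevant sections names the superiority population

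*SAP*

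**What the plan says.** **Lead set.** SAP 6.1: "All the main efficacy analyses will be performed on the PP population". Protocol 4.8.1: "All the main efficacy analyses will be performed on the PP population. Complementary efficacy analyses will be performed on the ITT-population for further confirmation". Neither sentence is limited to the non-inferiority test.

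**Agreement rule.** SAP 6.1: "The ITT and PP analyses will have to provide the same results to establish the non-inferiority". Protocol 4.8.1 has the same rule, and SAP 6.3.1 applies it to both lower confidence limits. Neither document has a counterpart for secondary endpoints.

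**Secondary endpoints.** SAP 6.3.2 analyses them "on both the PP population and the ITT population according to the statistical methods given in section 6.1". It ranks neither set. The tests are two-sided at 5% (SAP 6.1).

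**PP definition.** SAP 4.2 takes ITT subjects without significant violations and "with a wound area measurement at baseline and at week 6, or earlier if wound is healed prior to week 6". Protocol 4.8.1 defines PP as "all patients with a wound area measurement till the fourth week of follow-up, at least", excluding significant deviations. It has no healing exception.

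**Superiority.** Protocol 4.8.1 and SAP 6.1 give the criterion without naming a population. SAP 6.3.1 attaches it to ITT: "follow-up using PictZar on the ITT population does not overpass zero".

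**The concern.** Leading with PP is defensible for non-inferiority, where ITT has to agree. A test for a difference is another matter. There, removing subjects for what happened after randomisation can create or hide a difference, and the plan has no agreement rule to catch it.

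Under SAP 4.2, of two subjects who both stop at week 4, the healed one stays in PP and the unhealed one goes. If one arm loses more unhealed subjects, its PP mean improves relative to the other arm.

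Unequal loss is possible in this trial. It is open-label (protocol 4.1), the investigator may withdraw subjects at discretion (4.3.3), and the anticipated outcomes include prolonged healing, infection, maceration and dressing-related pain (4.6.6). At stake is a secondary advantage reported from the PP set while ITT shows none, with the plan's wording in support.

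**Working it through.** **1. Which set decides which question**

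| Question | Protocol 4.8.1 | SAP |
|---|---|---|
| Non-inferiority | PP leads; ITT must agree | PP and ITT limits must both pass (6.3.1) |
| Superiority | No set named; PP lead by default | None named in 6.1; ITT in 6.3.1 |
| Secondary difference tests | PP lead by default | Both sets run (6.3.2); none decisive; PP lead of 6.1 by default |
| PP membership | Area measured to week 4 at least | Week-6 area, or earlier if healed (4.2) |

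**2. The plan's own figure.** It supplies the group size used below. With margin 12, SD 35 and 80% power, n per group = 2 × 35² × (z₁₋α + 0.842)² / 12². One-sided α = 0.05 gives 106, as stated in both documents. One-sided α = 0.025, which matches the planned two-sided 95% interval, gives 134, and 106 per group then has 70.4% power. That is a separate matter; the present point does not depend on it.

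**3. Bias from dropping unhealed leavers.** Let d_E and d_A be the shares lost unhealed in the Exufiber and Aquacel Extra arms, and G the mean gap between retained subjects and leavers, equal in both arms. Each arm's all-randomised mean is its retained mean minus d × G. If the all-randomised difference is zero, then

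PP difference = (d_E − d_A) × G.

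The bias is zero when d_E = d_A.

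**4. False-advantage rate.** With 106 per arm and common SD, SE = SD × √[1/(106(1 − d_E)) + 1/(106(1 − d_A))], and P(lower 95% limit > 0) = 1 − Φ(1.96 − bias/SE). Only G/SD enters bias/SE. Setting SD = 35, the plan's value for percentage area reduction, therefore only fixes the scale. The documents give no SD for the secondary endpoints.

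Worked case, 15% versus 5%, G = 35 (1 SD): bias = 0.10 × 35 = 3.5; SE = 35 × √(1/90.1 + 1/100.7) = 5.08; 3.5/5.08 = 0.69; 1 − Φ(1.27) = 10.2%.

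| Lost unhealed (d_E vs d_A) | G = 17.5 (0.5 SD) | G = 35 (1 SD) | G = 70 (2 SD) |
|---|---|---|---|
| 10% vs 10% | bias 0; 2.5% | bias 0; 2.5% | bias 0; 2.5% |
| 15% vs 5% | bias 1.75; 5.3% | bias 3.5; 10.2% | bias 7.0; 28.1% |
| 20% vs 10% | bias 1.75; 5.2% | bias 3.5; 9.9% | bias 7.0; 26.8% |
| 20% vs 5% | bias 2.6; 7.3% | bias 5.25; 17.3% | bias 10.5; 53.0% |

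The loss rates and gaps are assumptions. The 20% ceiling is borrowed from protocol section 6, where dropout above 20% is a possible reason to discontinue the investigation. Reversing the arms reverses the sign.

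**5. A masked deficit.** The same algebra can hide a real disadvantage. With retained subjects at 45 points in both arms and leavers at 0, a 15% versus 5% loss gives −0.10 × 45 = −4.5 points in all randomised subjects and 0 in PP. A 10% versus 5% loss gives −2.25 and 0.

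**6. What ITT recovers.** SAP 4.1 requires at least one follow-up measurement, and LOCF supplies the week-6 value. An unhealed leaver who was measured returns to the comparison at the last observed value. One who was never measured does not.

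**The case against.** **The lead may not reach the secondary endpoints.** The PP sentence stands between the non-inferiority criterion and the agreement rule, and SAP 6.3.2 uses the word main for the week-6 time point. It could be read as covering the primary analysis alone. That reading is open, but the sentence speaks of all main efficacy analyses in the plural and no text limits it. Either way, nothing says which set decides when the two disagree.

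**Failures do not vanish from the secondary results.** A reader might infer that they do. The SAP also runs every secondary endpoint on ITT, with LOCF where applicable, so they drop out of the lead version only.

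**Superiority is not tested on the healed-or-week-6 set.** A reader might infer this by joining the protocol's silence to SAP 4.2. The documents do not support it. The protocol's PP set is a week-4 rule, so an unhealed subject who leaves after the week-4 measurement stays in with LOCF. The SAP's specific section puts superiority on ITT. What stands is that protocol superiority defaults to a set still selected after randomisation, and that the documents are not aligned.

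**A healed subject has completed.** Treatment runs to 6 weeks or healing, so SAP 4.2 keeps subjects whose endpoint was observed. That is a fair account of its purpose. It remains a completer set, biased when unhealed losses differ by arm.

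**The numbers show no actual bias.** Correct: they rest on assumed losses and gaps, and the documents report none by arm.

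**Conclusion.** The point holds as a gap in the decision rules. The secondary difference tests have a default lead set that SAP 4.2 selects partly on outcome, no rule settles a PP–ITT disagreement, and the superiority population is named only in SAP 6.3.1.

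The size depends on quantities the documents do not give. Over the assumed range, up to 20% versus 5% lost, bias runs from 0 to 10.5 points on a scale with SD 35. The one-directional false-positive rate runs from 2.5% to about 53%, and the upper end needs both a large imbalance and a 2 SD gap. The calculation assumes normality, a common SD and the same gap in both arms.

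The primary non-inferiority conclusion is not threatened by this, because PP alone cannot carry it. This is a cheap improvement, not a flaw in the main test.

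**What to change.** In protocol 4.8.1 and in SAP 6.1 and 6.3.2, replace the general lead-set sentence with:

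> Non-inferiority requires the criterion to be met in both PP and ITT. Superiority and all secondary tests for a difference are decided on ITT; PP results are supportive.

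Name ITT for superiority in protocol 4.8.1 and SAP 6.1 so that they match SAP 6.3.1. Reconcile the two PP definitions (week-4 rule versus week 6 or healed) so that both documents describe one set.

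The cost is wording, handled through the amendment route in protocol 4.9. Both sets are already analysed, so no new data or subjects are needed. Secondary estimates become slightly noisier. The change reduces the selection without removing it, because the planned ITT set still needs one follow-up measurement and relies on LOCF. Reporting, by arm, the number and reason for each exclusion from PP and ITT would let a reader judge what remains.
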